8. TRIAL DESIGN

8.1 Study Endpoints

8.1.1 Primary Efficacy Endpoint

- Percentage of subjects who become amenorrheic after one course of treatment

8.1.2 Secondary Endpoints

- Percentage of subjects who become amenorrheic after 2 courses of treatment
- Change and percentage change in PBAC score over the course of the study. Specifically comparing the baseline menstrual cycle to the matching end-of-study period leading up to Week 18 and the end of treatment as well as comparing the baseline PBAC to the ODI time periods.
- Percentage change in UFSQOL Symptom Severity score (UFS-SSS) comparing Week 18 to Baseline (three month look back) and for the ODI.
- Percentage change in the individual UFS-SSS subscores
- Percentage change from baseline in total uterine fibroid volume measured by MRI

8.2 Study Design

8.2.1 Overview of Study Design

This study is a phase 2 3-arm-study with a 36 week active dosing period. The study will be conducted in two stages.

[figure not shown]
[figure not shown]
[figure not shown]
In the first stage, women will undergo a baseline assessment period, with no treatment, until 15-20 days after the start of their second complete menstrual event. During this phase a pictorial blood loss assessment chart and daily diaries will be utilized. Used sanitary products from the first menstrual event will be collected and returned to the clinic for alkaline hematin assay. This assay will confirm subject eligibility (MBL must be 80 mL or greater by alkaline hematin assay for subjects to qualify).

In the second stage, subjects will be randomized into one of 3 arms in a 1-1-1 fashion. The start of the 18 week dosing period (Course 1) in this stage of the study should commence 15-20 days after the start of their first menses after Visit 2. Once active dosing is stopped, subjects will be followed until menses returns. The start of the second 18 week dosing period (Course 2) will commence 15-20 days after the start of their menses following withdrawal of drug after Course 1 has been completed. During the non dosing off-drug interval (ODI), subjects will continue to record study information in the daily paper diary and PBAC charts.

After end of dosing in Course 2, subjects will be followed through the subsequent recovery menses and for an additional 5 menstrual events, after which the subject may be offered the opportunity to enroll in an extension study. Subjects who fail to achieve amenorrhea may enroll in the extension study at Visit 19. Amenorrhea is defined as any 28-day period during treatment (not including the ODIs) without a bleeding score >1. Throughout the study women will record study information in the diary, PBAC and questionnaires as outlined in the study procedures.

In addition to the diary information, endometrial thickness will be recorded at screening and every month thereafter. Assessment of

trough levels of drug will be determined at every office visit during the first and second 18 week dosing periods.

The primary efficacy analysis will be conducted when all subjects complete the first cycle of treatment. A second analysis will summarize the subject's second treatment cycle which will be conducted after all subjects complete study treatment and follow-up.

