8.2.3 Randomization and Blinding

At Visit 3, subjects will be randomized to treatment in Arms 1, 2, or 3. Subjects will be treated with one capsule daily of 6 mg or 12 mg of Proellex, or placebo, which will be administered for a total of 36 weeks (two 18 week courses separated by an ODI) before the 6 cycle follow up is started. After the second treatment course is completed the subjects will be followed for 6 menstrual events to determine durability of effect of treatment, after which they may be offered the opportunity to enroll in an open-label extension study. Subjects who fail to achieve amenorrhea may enroll in the extension study at Visit 19. Amenorrhea is defined as any 28-day period during treatment (not including the ODIs) without a bleeding score >1. Each treatment course will be separated by an ODI. Blinded treatments kits will be randomized and distributed by the packaging company.

For the statistical analysis at the end of the first course of treatment, only statistical staff will be unblinded. All clinical operations staff and staff at investigative sites will remain blinded until completion of the study.

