12.2.2.1 Primary Endpoint: Incidence of Amenorrhea

The percentage of subjects who become amenorrheic during the 28 days leading up to the last day of dosing at Week 18 will be compared by Chi-Square test. Amenorrhea after a second course of treatment will be analyzed as a secondary endpoint. Testing will evaluate the pooled Proellex doses compared to placebo, each Proellex dose compared to Placebo as well as compare the active dose groups. A Fisher's Exact test will be utilized if the cell sizes are small.

A subject is deemed amenorrheic if they have no bleeding intensity score greater than 1 using the Daily Diary Card in [Appendix 3](#) (spotting not requiring hygiene products) during the 28 day period.

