12.2.2.2 Secondary Endpoints

Percentage Change in PBAC scores

The percentage change in PBAC scores over each 28 day period for each menstrual cycle will be recorded and compared to baseline to determine onset of benefit. Additionally PBAC scores will be used to monitor the level of vaginal bleeding during the ODI and the time to return to baseline vaginal bleeding to determine duration of benefit during the five menstrual cycle follow-up after dosing Course 2.

Within treatment group paired t-tests will evaluate treatment effect. Pairwise comparisons of the treatment groups will be made using a two-sample t-test as well as compare the pooled Proellex doses to placebo. While the primary assessment will be after 18 weeks of treatment, summaries will be prepared for each of the other visits. If data are missing, a last observation carried forward procedure will be used, including the baseline, if necessary. Non-parametric methods will be employed as appropriate.

Percentage change in total and individual symptom severity scores for the UFS-SSS

The UFS-SSS is an 8 question symptom severity score and has been validated as a three month look back questionnaire. The survey will be administered at the baseline of each dosing course and at the end of each course. An analysis of UFS-SSS scores will compare the pooled Proellex dose results to the placebo group with a t-test. Pairwise comparisons of the treatment groups will be made using a two-sample t-test. Within group paired tests will also be used to assess treatment effect. Non-parametric methods will be employed as appropriate. The primary assessment will be based on Visit 12 (after 18 weeks of treatment). If data are missing, a last observation carried forward procedure will be used, including the baseline, if necessary.

Percentage Change in Uterine Fibroid Volume by MRI

The percent change from baseline in total uterine fibroid volume will be determined at the end of each 18 week dosing course and after the 6 months of recovery menses (Visit 24). This study will assess up to 3 fibroids present at baseline in each subject. The volume of these 3 fibroids will be summed to determine the total uterine fibroid volume at each assessment.

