### 6.8.4 Uterine Fibroids

[figure not shown]
Uterine fibroid volume (by prolate ellipsoid method) will be determined by MRI. [REDACTED]

Total fibroid volume and percentage change in total fibroid volume will be summarized. Pairwise comparisons between groups will be performed using t-tests and Wilcoxon rank-sum tests, as appropriate. Statistical significance of the change from baseline within treatment groups will be determined using a paired t-test or Wilcoxon signed-rank test, as appropriate.

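### Women who never reach amenorrhea may roll over to open-label treatment at Visit 19, so exit from the durability follow-up depends on outcome, and carrying forward on-treatment values does not repair the later between-arm comparisons

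*Protocol*

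**What the plan says.** **Purpose.** Protocol 8.2.3: "After the second treatment course is completed the subjects will be followed for 6 menstrual events to determine durability of effect of treatment".

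**Exit.** Protocol 8.2.1, repeated in the synopsis and in 8.2.3, adds that "Subjects who fail to achieve amenorrhea may enroll in the extension study at Visit 19". For the other women, 8.2.3 places the offer after the six menses, when "they may be offered the opportunity to enroll in an open-label extension study".

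**Who counts as a failure for exit.** "Amenorrhea is defined as any 28-day period during treatment (not including the ODIs) without a bleeding score >1". This is wider than the primary endpoint in 12.2.2.1, which concerns "The percentage of subjects who become amenorrheic during the 28 days leading up to the last day of dosing at Week 18". Only a woman with no qualifying window in either course may leave early.

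**Comparisons after that point.**
- Fibroid volume: Protocol 12.2.2.2 has it determined "at the end of each 18 week dosing course and after the 6 months of recovery menses (Visit 24"), and says analyses go on at every volume assessment. SAP 6.8.4: "Pairwise comparisons between groups will be performed using t-tests and Wilcoxon rank-sum tests, as appropriate".
- UFS-SSS: SAP 6.8.3 covers each follow-up visit and provides for pairwise tests.
- PBAC: Protocol 12.2.2.2 uses it for the time until bleeding returns to baseline after Course 2.

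**Missing data.** Efficacy is analysed by ITT (Protocol 12.2.2, SAP 6.8). Protocol 12.3 completes the ITT data by last observation carried forward (LOCF). SAP 6.1 narrows this to the last observation on treatment. The readable text has no rule for women who roll over at Visit 19.

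**The concern.** Leaving the off-drug phase is tied to the outcome that the drug is meant to change. If the drug works, more placebo than active women are eligible to leave, and those who stay are no longer comparable by randomisation. Once a woman starts open-label treatment, her off-drug course cannot be observed, even if she still attends visits.

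The plan has only LOCF to meet this. For a Visit 19 leaver, the fibroid volume used at Visit 24 would be the value from the end of Course 2. That value describes the end of treatment, whereas the Visit 24 scan is meant to show what happens about six menses later. At stake is whether a Visit 24 or late-follow-up difference between arms, or its absence, can be read as evidence on durability.

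**Working it through.** **Inputs from the documents.** 15 women per arm, allocated 1:1:1 (Protocol 12.1, SAP 3.2); 3 × 15 = 45 evaluable. Two-sided 0.05 (Protocol 12.3, SAP 6.1). The readable text gives no amenorrhea rates, power or extension uptake, so there is no stated power figure to reproduce.

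**Assumptions.** p = amenorrhea rate under the exit definition: 10% placebo v 70% active, or 20% v 60%. u = share of eligible women who leave at Visit 19: 25% to 100%. Other dropout is ignored.

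**Formulas, per arm.**
- Still followed off drug: n = 15 × [p + (1 − p)(1 − u)]
- Share of the arm filled by LOCF under the written plan: (1 − p)u
- Amenorrheic share of those followed: 15p / n
- Standard error (SE) relative to 15 v 15, if only observed values are used: √(1/n₀ + 1/n₁) / √(2/15)

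Example, 10% v 70% with u = 50%: placebo 15 × (0.10 + 0.90 × 0.50) = 8.25; active 15 × (0.70 + 0.30 × 0.50) = 12.75; SE ratio √(1/8.25 + 1/12.75) / √(2/15) = 1.22.

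Each pair below is placebo v one active arm.

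| p | u | Still followed | Filled by LOCF | Amenorrheic among those followed | SE ratio |
|---|---|---|---|---|---|
| 10% v 70% | 25% | 11.6 v 13.9 | 22.5% v 7.5% | 13% v 76% | 1.09 |
| 10% v 70% | 50% | 8.25 v 12.75 | 45% v 15% | 18% v 82% | 1.22 |
| 10% v 70% | 100% | 1.5 v 10.5 | 90% v 30% | 100% v 100% | 2.39 |
| 20% v 60% | 50% | 9 v 12 | 40% v 20% | 33% v 75% | 1.21 |
| 20% v 60% | 100% | 3 v 9 | 80% v 40% | 100% v 100% | 1.83 |

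At 10% placebo amenorrhea and full uptake, the chance that no placebo woman remains is 0.9¹⁵ = 0.21.

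**Precision, observed values only.** Take an illustrative difference of 1 SD, pooled active v placebo, with power ≈ Φ(1/√(1/n₀ + 1/n₁) − 1.96). With nobody leaving, 15 v 30 gives 0.89. At 10% v 70%, 50% uptake (8.25 v 25.5) gives 0.70 and full uptake (1.5 v 21) gives 0.22.

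**Bias under the written LOCF rule.** Let d be the mean gap, among an arm's leavers, between the last on-treatment value and the off-drug value they would have had. The Visit 24 difference (active − placebo) is shifted by (1 − p_A)u·d_A − (1 − p_P)u·d_P. At 10% v 70% that is 0.15·d_A − 0.45·d_P at 50% uptake, and 0.30·d_A − 0.90·d_P at full uptake. It vanishes only if the weighted gaps happen to cancel. In active arms, d includes any partial on-drug effect that would have faded; in placebo, it reflects change over time. The documents do not fix the net sign.

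**The case against.** Several points on the other side stand.

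- **Leavers are not dropped.** A reader might infer that the later analyses cover responders only, so that durability is inflated by a missing denominator. The plan is ITT with LOCF, so leavers stay in with a carried-forward value. The counts and SE ratios above describe the observed data. The flaw in the written analysis is what is carried forward.
- **The control is not necessarily lost.** A reader might infer that the placebo arm empties. Exit is optional and uptake is not stated. At 50% uptake about 8 of 15 placebo women remain, and only about 18% of them are amenorrheic under the first assumption. The description 'mainly responders' fits the active arms; it fits the remaining placebo women only when uptake is very high.
- **The main questions are untouched.** The primary endpoint, amenorrhea after two courses, and the assessments after 18 weeks all precede Visit 19. Protocol 8.1.2 does not name durability as an endpoint, and this is a small Phase 2 trial.
- **Some text cannot be read.** The PBAC intervals in SAP 6.8.2 and part of SAP 6.8.4 are not visible, and a roll-over rule could sit in withheld text. The evidence for between-arm testing in this period is firmest for UFS-SSS and fibroid volume.

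These points limit the size of the concern without removing it. Durability is the stated reason for the follow-up, tests between arms extend into it, and neither omitting leavers nor carrying forward on-treatment values gives a randomised comparison of off-drug durability.

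**Conclusion.** The concern holds as a moderate issue limited to durability. Exit at Visit 19 is outcome-dependent and, if the drug works, arm-dependent. The between-arm comparisons of post-Course-2 UFS-SSS, return of PBAC to baseline and Visit 24 fibroid volume are therefore compromised, and could be lost if uptake is high. Under the assumed rates, the share of an arm resting on carried-forward values runs from 22.5% placebo v 7.5% active at 25% uptake to 90% v 30% at full uptake.

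This rests on the assumed rates and uptake, on 15 women per arm, and on the absence of a roll-over rule in text that cannot be read. The documents do not support the stronger conclusions that the placebo control is certain to disappear, or that the trial's primary result is affected.

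**What to change.** Leave the roll-over rule as it is and change the analysis wording in Protocol 12.2.2.2 and 12.3 and SAP 6.1 and 6.8:

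1. State that on-treatment LOCF is not used for off-drug follow-up time points.
2. For any between-arm durability comparison, keep every ITT woman in the denominator and count those who roll over at Visit 19 as non-durable. Use observed follow-up for every woman who stays, including those not amenorrheic in the last 28 days of Course 2. Define a durable outcome in advance, and give a rule for women who stay but lack the follow-up measurement.
3. Label PBAC, UFS-SSS and fibroid volume results after Visit 19 as descriptive among women still followed, without between-arm p-values. Report by arm and amenorrhea status how many left at Visit 19.

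**Cost.** Wording only, with no new visits or measurements. The stated durability rate will be lower and the Visit 24 p-values are given up. The comparison in item 2 measures response and persistence together, and it scores a leaver with a partial reduction in bleeding as a failure. The report should say so.

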8.2.2 Study Drug Accountability

The designee assigned by the Principal Investigator at each site will maintain accurate records of receipt of all study drugs, including dates of receipt. Reasons for deviation from the expected dispensing

regimen must also be recorded. A Drug Dispensing Form will be provided for this purpose. To satisfy regulatory requirements regarding drug accountability and destruction, the Principal Investigator at each site will return all used, unused, empty, and partially used study medication with dispensing records to the Sponsor for final accountability and disposal, after accountability has been verified by the study monitor.

8.2.3 Randomization and Blinding

At Visit 3, subjects will be randomized to treatment in Arms 1, 2, or 3. Subjects will be treated with one capsule daily of 6 mg or 12 mg of Proellex, or placebo, which will be administered for a total of 36 weeks (two 18 week courses separated by an ODI) before the 6 cycle follow up is started. After the second treatment course is completed the subjects will be followed for 6 menstrual events to determine durability of effect of treatment, after which they may be offered the opportunity to enroll in an open-label extension study. Subjects who fail to achieve amenorrhea may enroll in the extension study at Visit 19. Amenorrhea is defined as any 28-day period during treatment (not including the ODIs) without a bleeding score >1. Each treatment course will be separated by an ODI. Blinded treatments kits will be randomized and distributed by the packaging company.

For the statistical analysis at the end of the first course of treatment, only statistical staff will be unblinded. All clinical operations staff and staff at investigative sites will remain blinded until completion of the study.

8.2.4 Study Medication

All study drugs will be supplied by Repos Therapeutics Inc. Test drug, Proellex, will be supplied as placebo, 6, and 12 mg vaginal capsules, in blister packs of 10 capsules, by a clinical supplies contract vendor designated by Repos Therapeutics Inc. [REDACTED]

[REDACTED] instructions to administer 1 capsule vaginally each day at the same time using the applicator provided. Subjects should be instructed to refrain from vaginal intercourse or putting anything in the vagina for 48 hours prior to clinic visits 2, 3, 12, and 18. Study medication should be taken at the same time of day every day, and clinic visits should be scheduled according to each subject's administration schedule. [REDACTED]

[REDACTED]

8.2.5

[REDACTED]

[REDACTED]

[REDACTED]

[REDACTED]

8.2.6

[REDACTED]

[REDACTED]

[REDACTED]

8.3

[figure not shown]
[REDACTED]

[figure not shown]
8.3.1 Inclusion Criteria

Subjects must meet the following criteria:

- Otherwise healthy adult females between 18 and 47 years
- Subject has a history of at least 3 regular menstrual cycles in which menorrhagia is due to uterine fibroids (a past or concurrent diagnosis of uterine fibroids is acceptable).
- Screening ultrasound confirms presence of uterine fibroids

- Agreement not to attempt to become pregnant during the trial

- Agreement to use only sanitary pads provided throughout the course of the study, tampon use is prohibited
- Ability to complete a daily subject diary and study procedures in compliance with the protocol

- Has a negative pregnancy test at the Screening and Baseline visits
- A Body Mass Index (BMI) between 18 and 45 inclusive
- Subject is available for all treatment and follow-up visits

8.3.2 Exclusion Criteria

Subjects meeting any of the following criteria will be excluded from the study:

- Subject is a post-menopausal woman, defined as either; six (6) months or more (immediately prior to screening visit) without a menstrual period, or prior hysterectomy and/or oophorectomy.
- Subject is pregnant or lactating or is attempting or expecting to become pregnant during the entire study period

- Received an investigational drug in the 30 days prior to the screening for this study
- Subject has a history of PCOS
- Concurrent use of any testosterone, progestin, androgen, estrogen, anabolic steroids, DHEA or hormonal products for at least 2 weeks

prior to screening and during the study, including the [REDACTED]
[REDACTED]

[figure not shown]
- Use of oral contraceptives in the 30 days preceding screening. Use of Depo-Provera® in the preceding 10 months.
- Use of GnRHAs (e.g. Lupron Depot) within 3 months prior to screening (Lupron Depot must have a wash-out period of 3 months prior to screening)
- Has an IUD in place
- History or current diagnosis of malignancy other than curatively treated basal cell carcinoma

[figure not shown]
[REDACTED]

[figure not shown]
- Recent history (within past 6 months) of alcoholism or drug abuse

[figure not shown]
[REDACTED]

[figure not shown]
- Clinically significant abnormal findings on screening examination and laboratory assessments or any condition which in the opinion of the investigator would interfere with the participant's ability to comply with the study instructions or endanger the participant if she took part in the study

[figure not shown]

10. ASSESSMENT OF SAFETY

10.1 Adverse Events

10.1.1 Reporting Adverse Experiences

Any AE (clinical sign, symptom, or disease) temporally associated with the use of this investigational drug, whether or not considered related to the investigational product, shall be documented on the CRF and eDC. All SAEs and AEs reported by the subject or observed by the Principal Investigator for up to 30 days after the last dose of study medication will be individually listed. After Visit 20, all SAEs and any adverse events that the investigator considers to be due to the study drug (e.g. hepatotoxicity) and not those considered to be due to withdrawal of the drug (e.g. vaginal bleeding), will be collected. The signs and symptoms, time of onset (24-hour clock), duration, action taken and follow-up procedures will be reported.

10.1.2 Definitions

Adverse Event – Any untoward medical occurrence in a clinical investigation subject administered a drug and does not necessarily have a causal relationship with this treatment. An AE can therefore, be any unfavorable and unintended sign (including an abnormal laboratory finding), symptom, or disease temporally associated with the use of an investigational product, whether or not related to the investigational product.

Serious Adverse Event (SAE) – An adverse drug experience that results in any of the following outcomes: death, a life-threatening experience, requires or prolongs subject hospitalization, results in persistent or significant disability/incapacity, or is a congenital anomaly or birth defect.

Cases of liver transaminases that increase above 3 times the upper limit of normal must be reported as SAEs regardless of whether the above defined SAE criteria are met.

Unexpected Adverse Event: Any adverse event that is not identified in nature, severity, or frequency in the current Investigator's Brochure.

Additionally, the Principal Investigator will evaluate all AEs as follows:

Action taken: whether or not the AE caused the subject/patient to discontinue the study medication.

Intensity, to be graded as:

DEGREE	DESCRIPTION
Mild	Awareness of signs and symptoms; easily tolerated
Moderate	Discomfort sufficient to interfere, but not prevent daily activity
Severe	Unable to carry out usual activity

Relationship to study medication, to be graded as:

DEGREE	DESCRIPTION
Definitely	There is evidence of exposure to the study drug, for example, reliable history or acceptable compliance assessment; the temporal sequence of the AE onset relative to the medication is reasonable; the AE is most likely to be explained by the treatment than by another cause; the AE shows a pattern consistent with previous knowledge of the treatment.
Probably	There is evidence of exposure to the study drug; the temporal sequence of the AE onset relative to medication administration is reasonable; the AE is more likely explained by the treatment than by another cause.
Possibly	There is evidence of exposure to the study drug; the temporal sequence of the AE relative to the medication administration is reasonable; the AE could have been due to another equally likely cause.
Not Related	There is evidence of exposure to the study drug; there is another more likely cause of the AE.

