6.6 Ethical Conduct of the Study

This trial will be conducted in strict compliance with the protocol and all applicable FDA regulations and GCP guidelines to insure Good Clinical Practice standards. IntegReview, [name], will serve as an Institutional Review Board (IRB) for clinical sites who will accept their review.

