10.1.3 Serious Adverse Events (SAEs)

The Principal Investigator shall document all SAEs in a subject receiving study drug until completion of the study and must be reported to the Repos Therapeutics Inc. Safety Monitor within 24 hours by Fax or telephone, even if the SAE does not appear to be drug-related. This report should include all available information at the time of notification. This notification should be followed with submitting a SAE Report Form provided by Repos Therapeutics Inc, and notifying the IRB.

All additional follow-up reports must be reported to the Repos Therapeutic Inc. monitor as soon as available.

[figure not shown]
Cases of liver transaminases that increase above 3 times the upper limit of normal must be reported as SAEs regardless of whether the above defined SAE criteria are met.

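### The SAE definition has no important-medical-event category, so some events managed without admission can miss 24-hour reporting and, after Visit 20, may not be collected at all

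*Protocol*

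**What the plan says.** Protocol section 10.1.2 defines an SAE as "An adverse drug experience that results in any of the following outcomes: death, a life-threatening experience, requires or prolongs subject hospitalization", and the sentence ends "results in persistent or significant disability/incapacity, or is a congenital anomaly or birth defect". The sentence is complete and carries no redaction mark. The section then adds one event by rule: transaminases above 3 times the upper limit of normal "must be reported as SAEs regardless of whether the above defined SAE criteria are met". The liver rule also appears in the laboratory notes after the synopsis and in section 10.1.3.

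Three things depend on SAE status:

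- **Expedited reporting.** Section 10.1.3 requires SAEs to go to the sponsor's "Safety Monitor within 24 hours by Fax or telephone, even if the SAE does not appear to be drug-related". An SAE form and notice to the IRB follow.
- **Collection late in follow-up.** Section 10.1.1 says that any AE "shall be documented on the CRF and eDC", and the visible text sets no time limit for this. After Visit 20 collection narrows to SAEs and to AEs the investigator attributes to the study drug. Events put down to drug withdrawal are left out, with vaginal bleeding given as the example.
- **Analysis.** SAP section 6.9.1 summarises serious TEAEs separately. The visible SAP has no definition of serious of its own.

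**The concern.** An event can matter medically without causing death, admission, disability or a birth defect, and without being judged life-threatening. The protocol accepts this for the liver, since the transaminase rule exists to catch events that the five outcomes would miss. The visible text makes no such provision for anything else.

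The population and the monitoring make the gap practical. All participants have menorrhagia, and drug is withdrawn after each course so that menses return. Section 8.2.1 has endometrial thickness recorded every month, and the synopsis lists colposcopy findings among the safety assessments. Bleeding and surveillance findings can both be handled entirely in outpatient care.

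At stake is how soon the sponsor and the IRB learn of such an event while other women may still be dosing. Late in follow-up, the question is whether it enters the data at all. SAP section 6.2 limits the first planned analysis to efficacy endpoints, so the first planned safety tabulation comes after all subjects have finished.

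There is also a wording conflict. The SAE definition opens with a term that can be read as implying drug causation. The AE definition just above it disregards relatedness, and 10.1.3 requires a report "even if the SAE does not appear to be drug-related".

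**Working it through.** No statistical calculation applies. The check is to count the criteria and run typical events through the rules as written.

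**Count, from section 10.1.2.** Outcomes: death; life-threatening experience; hospitalization required or prolonged; persistent or significant disability or incapacity; congenital anomaly or birth defect. That is 5. Events added by rule: transaminases above 3 times the upper limit of normal, 1. Total 5 + 1 = 6. Criteria for important medical events, or for intervention to prevent a listed outcome: 0.

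**Events run through 10.1.1, 10.1.2 and 10.1.3.**

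1. *Symptom-free ALT just above 3 times the upper limit.* It meets none of the five outcomes but is caught by the liver rule. A 24-hour report is due.
2. *Heavy bleed treated without admission, judged neither life-threatening nor disabling, before the Visit 20 cut-off.* It meets no criterion. It goes on the CRF and eDC as an AE, with no 24-hour report and no IRB notice under 10.1.3. In the SAP it counts as a TEAE and by maximum severity, but not as serious.
3. *The same bleed after Visit 20, attributed to drug withdrawal.* It is not an SAE and is not attributed to the drug, and 10.1.1 excludes withdrawal bleeding. It is not collected.
4. *Significant finding on endometrial or colposcopic surveillance, managed as an outpatient and judged unrelated.* Before the cut-off it is handled as in case 2. After Visit 20 it is not collected, because it is neither serious under the list nor attributed to the drug.
5. *Bleed treated without admission but judged life-threatening.* It is an SAE under the second outcome and is reported within 24 hours.

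Cases 1 and 5 show where the rules work. Cases 2 to 4 show the gap: SAE status decides the speed of reporting before Visit 20 and, for events not attributed to the drug, decides collection itself afterwards.

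**The case against.** **Some outpatient events still qualify.** The life-threatening and disability criteria do not require admission, so a bleed needing emergency treatment, or a cancer, can be an SAE on the investigator's judgment. This stands. A reader might infer that every outpatient-managed event escapes, whatever its gravity; the definition does not support that. The gap covers events below those two thresholds.

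**Malignancy and transfusion are not named risks.** This also stands. A reader might infer from the exclusion criteria and the monthly endometrial measurement that the protocol identifies cancer as a risk of treatment. The visible text mentions malignancy only as an exclusion and never mentions transfusion. Both serve only as illustrations. Heavy bleeding has a firmer basis, through 10.1.1 and the Amendment 2 summary of changes, where it is a reason for discontinuation.

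**There are other safeguards.** AEs go on the CRF, the sponsor's monitors review progress periodically (13.3), diaries and PBAC run throughout, and SAP 6.9.1 lists all AEs. These make it likely that an event before the Visit 20 cut-off is eventually seen. They set no reporting clock, and an AE listing cannot show an event that 10.1.1 does not collect. By then dosing is over for the woman concerned, which limits the consequence for her but not for the trial's safety record.

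**Redacted text may hold more rules.** Sections 8.2.5, 8.2.6 and the body of 8.3 are blacked out, and part of 10.1.3 is not shown. Special reporting rules there cannot be excluded.

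**The protocol commits to act** "in strict compliance with the protocol and all applicable FDA regulations and GCP guidelines". That general commitment does not change the definition a site would apply when deciding whether an event is an SAE.

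**The causality wording is harmless.** Largely so, because 10.1.3 settles the reporting duty. It remains an inconsistency that can be removed in the same edit.

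**Conclusion.** The point holds in a limited form. The SAE definition is a closed list of five outcomes plus one liver rule, with no important-medical-event category. An event managed without admission, and not judged life-threatening or disabling, can miss the 24-hour report, the IRB notice and the serious-TEAE table. After Visit 20, if it is also not attributed to the drug, it may not be collected at all.

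No numerical size can be given. The documents state no frequency for such events, and the share that one subject contributes to an arm of 15 would not measure the gap. The safety comparison is descriptive in any case. The conclusion assumes that sites apply 10.1.2 as written and that the redacted sections add no further reporting rules. If they do, those rules should be cross-referenced in 10.1.2.

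**What to change.** In section 10.1.2:

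- Replace the opening words, 'An adverse drug experience', with 'Any adverse event, whether or not considered related', so that the definition agrees with the AE definition and with 10.1.3.
- Add a sixth criterion: an important medical event that, in the investigator's judgment, may jeopardize the subject or require intervention to prevent one of the listed outcomes. New malignancy and transfusion for bleeding may be given as examples. A list of always-reportable events is optional once the general criterion exists.

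Because 10.1.1 collects all SAEs after Visit 20, the new criterion also brings events that meet it back into collection there. Section 10.1.1 should state that the exclusion of withdrawal bleeding does not apply to an event meeting any SAE criterion. SAP 6.9.1 needs no new analysis, only a reference to the revised definition.

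The cost is one paragraph in an amendment and a matching line on the SAE form, then a few more expedited reports and a slightly higher SAE count. The change affects reporting only, not dosing or clinical management.
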